Appendix 7.3 1-
month post-ROR Survey

1. Please identify the individual completing this survey.

- Mother
- Father
- Other (please specify): _____

2. In the past 3 months, has your marital status or employment changed?

- Yes
- No

If you answered yes to question 2:

3. Are you currently (please select one):

- Married
- Living together but not married
- Separated or Divorced
- Widowed
- Never married and currently not living together

If answered yes to question 2:

4. What is your employment status from this past week? (select all that apply)

- No change
- Working for pay at a job or business
- With a job or business but not at work
- Looking for work
- Working, but not for pay, at a family-owned job or business
- Not working at a job or business
- Not looking for work
- Taking care of house or family
- Going to school
- Retired
- Disabled
- Other: _____
- Refused
- Don't know

5. In the past month, has your residential address changed?

- Yes
- No

If you answered yes to question 5:

6. What is the address where you currently live?

Street: _____

City: _____

State: _____

Zip Code: _____

SouthSeq 1-month post-ROR Survey

7. In the past month, has your child's residential address changed?

- Yes
- No

If you answered yes to question 7:

8. What is the address where your child currently lives?

Street: _____

[figure not shown]
City: _____ State: _____ Zip Code: _____

How good is your child's health TODAY?

- We would like know how good or bad your child's health is **TODAY**.
- This line is numbered **0** to **100**.
- **100** means the best health you can imagine. **0** means the worst health you can imagine.
- Mark an X on the scale to indicate how your child's health is **TODAY**
- Now please write the number you marked on the scale in the box below

YOUR CHILD'S HEALTH TODAY= _____

- **N/A**

9. Considering your child's medical condition, please rank the degree to which you agree with the following statements:

	Strongly Disagree	Disagree	Somewhat Disagree	Neutral	Somewhat Agree	Agree	Strongly Agree
I am clear in my own mind why my family has enrolled in SouthSeq.							
I can explain what the condition means to people in my family who may need to know.							
I understand the impact of the condition on my child(ren)/any child I may have.							
When I think about the condition in my family, I get upset.							
I don't know where to go to get the medical help I/my family need (s).							
I can see that good things have come from having this condition in my family.							
I can control how this condition affects my family.							
I feel positive about the future.							
I am able to cope with having this condition in my family.							
I don't know what could be gained from each of the options available to me.							
Having this condition in my family makes me feel anxious.							
I don't know if this condition could affect my other relatives (brothers, sisters, aunts, uncles, cousins).							

SouthSeq 1-month post-ROR Survey

In relation to the condition in my family, nothing I decide will change the future for my children/any children I might have.							
I understand the reasons why my child's doctor referred my family to SouthSeq							
I know how to get the non-medical help I/my family need(s) (e.g. educational, financial, social support).							
I can explain what the condition means to people outside my family who may need to know (e.g. teachers, social workers).							
I don't know what I can do to change how this condition affects me/my children.							
I don't know who else in my family might be at risk for this condition.							
I am hopeful that my child(ren) can look forward to a rewarding family life.							
I am able to make plans for the future.							
I feel guilty because I (might have) passed this condition on to my children.							
I am powerless to do anything about this condition in my family.							

10. The following questions ask about how you, as a parent, felt after receiving your child's genetic test results. Please indicate how much you had each specific feeling in the past week by choosing the one answer for each question.

SouthSeq 1-month post-ROR Survey

	Not at all	A little	Somewhat	A good deal	A great deal
How upset did you feel about your child's genetic test result?					
How happy did you feel about your child's genetic test result?					
How anxious or nervous did you feel about your child's genetic test result?					
How relieved did you feel about your child's genetic test result?					
How sad did you feel about your child's genetic test result?					
How frustrated did you feel about recommendations for your child's care based on the genetic test?					
How uncertain did you feel about what your child's genetic test result means for your child?					
How uncertain did you feel about what your child's genetic test result means for other family members' risk of disease?					
How much did you feel that you understood clearly your child's choices for care based on the genetic test result?					
How concerned did you feel that your child's genetic test result would affect his or her ability to get or keep health insurance?					
How helpful was the information you received from your genetic test result in planning for your child's future?					
How concerned did you feel that your child's genetic test result might make it hard for them to get or keep a job?					

How guilty did you feel about your child's genetic test result?					
How much loss of control over your child's life did you feel because of your child's genetic test result?					

11. Rate how certain you feel about the following aspects of your child's sequence results:

	Very Uncertain (1)	2	3	4	Very Certain (5)
What my child's test results mean for his/her health					
What actions I need to take based on my child's test results					
How my child's doctor may use the results to improve my child's health					
Whether I am worried or concerned about my child's test results					
Whether my child's test results revealed something alarming					
Whether my child's test results disrupted my life					
Whether I can trust my child's test results					
Whether my child's test results are accurate					

12. Please indicate how useful you find the following outcomes of genome sequencing for you and your child

	Not at all useful (1)	A little useful (2)	Somewhat useful (3)	Neutral (4)	Useful (5)	Very useful (6)	Extremely useful (7)

SouthSeq 1-month post-ROR Survey

Help with my child's life planning						
Inform plans for my child's school or career						
Inform my child's decisions about having children						
Use for testing a future pregnancy, if appropriate						
Help me or our family mentally prepare for the future						
Help to better understand my child's health						
Contribute to my child's self-knowledge						
Help me cope with my child's health risks						
Help me feel more in control of my child's health						
Help me feel more in control of my child's life						
Simply to provide information						
Satisfy my curiosity about my child						
Help my child use social programs, like resources or services						
Improve communication with my family members						
Feel good about helping the medical community						
Feel good about having information for family members						

Feel good about taking responsibility for my child's health							
---	--	--	--	--	--	--	--

13.

a. **In general, would you say your health is:**

Excellent	Very Good	Good	Fair	Poor

14. **How well do you understand your child's test results?**

Not at all	A little bit	Moderately	Quite a bit	Extremely

15. **Please tell us about your experience receiving your child's genetic test results.**

	Strongly Disagree	Disagree	Neither Agree nor Disagree	Agree	Strongly Agree	Not Applicable
I was treated with sensitivity and respect.						
I felt listened to.						
The clinical team checked to make sure I understood the information						
I trust the clinical team						
The clinical team explained complicated topics well						
I got clear, understandable information.						
I received too much information to understand						

SouthSeq 1-month post-ROR Survey

It was hard to make sense out of the information						
I felt I had the information and support available to me to answer any questions I had after receiving my child's genetic results						
I felt comfortable asking questions and voicing my concerns						
The clinical team helped me cope with any uncertainty or unknowns						
It was hard to ask questions about this information						
I felt comfortable talking about sensitive issues or embarrassing subjects with the clinical team						
The clinical team noticed when I had problems understanding						
I had questions about this information that I was unable to ask						

16. **Here are some questions about the support that is available to you**

a. About how many close friends and close relatives do you have (people you feel at ease with and can talk to about what is on your mind)?

Write in number of close friends and close relatives: _____

b. People sometimes look to others for companionship, assistance, or other types of support. How often is each of the following kinds of support available to YOU if you need it?

	None of the time	A little of the time	Some of the time	Most of the time	All of the time
Someone to help you if you were confined to bed...					
Someone you can count on to listen to you when you need to talk...					
Someone to give you good advice about a crisis...					
Someone to take you to the doctor if you needed it...					
Someone who shows you love and affection...					
Someone to have a good time with...					
Someone to give you information to help you understand a situation...					
Someone to confide in or talk to about yourself or your problems...					
Someone who hugs you...					
Someone to get together with for relaxation...					
Someone to prepare your meals if you were unable to do it yourself...					
Someone whose advice you really want...					
Someone to do things with to help you get your mind off things...					
Someone to help with daily chores if you were sick...					
Someone to share your most private worries and fears with...					
Someone to turn to for suggestions about how to deal with a personal problem...					
Someone to do something enjoyable with...					
Someone who understands your problems...					
Someone to love and make you feel wanted...					

17. Which of the following sources, if any, did you use to find more information about the genetic test results you received at your last visit?

Please rate the usefulness of the sources you used. (1-not useful at all, 5=very useful)

	Not useful at all (1)	2	3	4	Very useful (5)	N/A
Family or friends	o	o	o	o	o	o
Facebook	o	o	o	o	o	o
Support groups	o	o	o	o	o	o
My/my child's other doctors	o	o	o	o	o	o
Internet search (i.e. Google, PubMed, etc.)	o	o	o	o	o	o
Books and other print media	o	o	o	o	o	o
Information provided by the doctor who ordered my child's genetic test	o	o	o	o	o	o
Other (please specify):	o	o	o	o	o	o
None	o	o	o	o	o	o

Appendix 7.4 and 7.5
4-month and 4-month plus post-ROR Survey

1. Please identify the individual completing this survey.

- Mother
- Father
- Other (please specify): _____

2. In the past 3 months, has your marital status or employment changed?

- Yes
- No

If you answered yes to question 2:

3. Are you currently (please select one):

- Married
- Living together but not married
- Separated or Divorced
- Widowed
- Never married and currently not living together

If answered yes to question 2:

4. What is your employment status from this past week? (select all that apply)

- No change
- Working for pay at a job or business
- With a job or business but not at work
- Looking for work
- Working, but not for pay, at a family-owned job or business
- Not working at a job or business
- Not looking for work
- Taking care of house or family
- Going to school
- Retired
- Disabled
- Other: _____
- Refused
- Don't know

5. In the past month, has your residential address changed?

- Yes
- No

If you answered yes to question 5:

6. What is the address where you currently live?

Street: _____

City: _____ State: _____ Zip Code: _____

SouthSeq 4-month post-ROR Survey

7. In the past month, has your child's residential address changed?

- Yes
- No

If you answered yes to question 7:

8. What is the address where your child currently lives?

Street: _____

[figure not shown]
City: _____ State: _____ Zip Code: _____

How good is your child's health TODAY?

- We would like know how good or bad your child's health is **TODAY**.
- This line is numbered **0** to **100**.
- **100** means the best health you can imagine. **0** means the worst health you can imagine.
- Mark an X on the scale to indicate how your child's health is **TODAY**
- Now please write the number you marked on the scale in the box below

YOUR CHILD'S HEALTH TODAY= _____

- N/A

9. Considering your child's medical condition, please rank the degree to which you agree with the following statements:

	Strongly Disagree	Disagree	Somewhat Disagree	Neutral	Somewhat Agree	Agree	Strongly Agree
I am clear in my own mind why my family has enrolled in SouthSeq.							
I can explain what the condition means to people in my family who may need to know.							
I understand the impact of the condition on my child(ren)/any child I may have.							
When I think about the condition in my family, I get upset.							
I don't know where to go to get the medical help I/my family need (s).							
I can see that good things have come from having this condition in my family.							
I can control how this condition affects my family.							
I feel positive about the future.							
I am able to cope with having this condition in my family.							
I don't know what could be gained from each of the options available to me.							
Having this condition in my family makes me feel anxious.							
I don't know if this condition could affect my other relatives (brothers, sisters, aunts, uncles, cousins).							

SouthSeq 4-month post-ROR Survey

In relation to the condition in my family, nothing I decide will change the future for my children/any children I might have.							
I understand the reasons why my child's doctor referred my family to SouthSeq							
I know how to get the non-medical help I/my family need(s) (e.g. educational, financial, social support).							
I can explain what the condition means to people outside my family who may need to know (e.g. teachers, social workers).							
I don't know what I can do to change how this condition affects me/my children.							
I don't know who else in my family might be at risk for this condition.							
I am hopeful that my child(ren) can look forward to a rewarding family life.							
I am able to make plans for the future.							
I feel guilty because I (might have) passed this condition on to my children.							
I am powerless to do anything about this condition in my family.							

10. The following questions ask about how you, as a parent, felt after receiving your child's genetic test results. Please indicate how much you had each specific feeling in the past week by choosing the one answer for each question.

SouthSeq 4-month post-ROR Survey

	Not at all	A little	Somewhat	A good deal	A great deal
How upset did you feel about your child's genetic test result?					
How happy did you feel about your child's genetic test result?					
How anxious or nervous did you feel about your child's genetic test result?					
How relieved did you feel about your child's genetic test result?					
How sad did you feel about your child's genetic test result?					
How frustrated did you feel about recommendations for your child's care based on the genetic test?					
How uncertain did you feel about what your child's genetic test result means for your child?					
How uncertain did you feel about what your child's genetic test result means for other family members' risk of disease?					
How much did you feel that you understood clearly your child's choices for care based on the genetic test result?					
How concerned did you feel that your child's genetic test result would affect his or her ability to get or keep health insurance?					
How helpful was the information you received from your genetic test result in planning for your child's future?					
How concerned did you feel that your child's genetic test result might make it hard for them to get or keep a job?					

How guilty did you feel about your child's genetic test result?					
How much loss of control over your child's life did you feel because of your child's genetic test result?					

11. Rate how certain you feel about the following aspects of your child's sequence

a. In general, would you say your health is:

Excellent	Very Good	Good	Fair	Poor

12. How well do you understand your child's test results?

Not at all	A little bit	Moderately	Quite a bit	Extremely

13. Please tell us about your experience receiving your child's genetic test results.

	Strongly Disagree	Disagree	Neither Agree nor Disagree	Agree	Strongly Agree	Not Applicable
I was treated with sensitivity and respect.						
I felt listened to.						
The clinical team checked to make sure I understood the information						
I trust the clinical team						
The clinical team explained complicated topics well						
I got clear, understandable information.						

SouthSeq 4-month post-ROR Survey

I received too much information to understand						
It was hard to make sense out of the information						
I felt I had the information and support available to me to answer any questions I had after receiving my child's genetic results						
I felt comfortable asking questions and voicing my concerns						
The clinical team helped me cope with any uncertainty or unknowns						
It was hard to ask questions about this information						
I felt comfortable talking about sensitive issues or embarrassing subjects with the clinical team						
The clinical team noticed when I had problems understanding						
I had questions about this information that I was unable to ask						

14. **Here are some questions about the support that is available to you**

a. About how many close friends and close relatives do you have (people you feel at ease with and can talk to about what is on your mind)?

Write in number of close friends and close relatives: _____

b. People sometimes look to others for companionship, assistance, or other types of support. How often is each of the following kinds of support available to YOU if you need it?

	None of the time	A little of the time	Some of the time	Most of the time	All of the time
Someone to help you if you were confined to bed...					
Someone you can count on to listen to you when you need to talk...					
Someone to give you good advice about a crisis...					
Someone to take you to the doctor if you needed it...					
Someone who shows you love and affection...					
Someone to have a good time with...					
Someone to give you information to help you understand a situation...					
Someone to confide in or talk to about yourself or your problems...					
Someone who hugs you...					
Someone to get together with for relaxation...					
Someone to prepare your meals if you were unable to do it yourself...					
Someone whose advice you really want...					
Someone to do things with to help you get your mind off things...					
Someone to help with daily chores if you were sick...					
Someone to share your most private worries and fears with...					
Someone to turn to for suggestions about how to deal with a personal problem...					
Someone to do something enjoyable with...					
Someone who understands your problems...					
Someone to love and make you feel wanted...					

15. Which of the following sources, if any, did you use to find more information about the genetic test results you received at your last visit?

Please rate the usefulness of the sources you used. (1=not useful at all, 5=very useful)

	Not useful at all (1)	2	3	4	Very useful (5)	N/A
Family or friends						
Facebook						
Support groups						
My/my child's other doctors						
Internet search (i.e. Google, PubMed, etc.)						
Books and other print media						
Information provided by the doctor who ordered my child's genetic test						
Other (please specify):						
None						

16. Since receiving your child's study results, did you share the information with any biological family members (blood relatives)?

- Yes
- I didn't share this information with anyone (if selected, skip to question 20)
- I haven't shared this information yet, but plan to in the future (if selected, skip to question 18)
- I do not have blood relatives to share this information with (if selected, skip all remaining questions)

17. Since receiving your child's study results, have you shared the information with any of the following blood relatives?

	Yes	No	N/A
My child's other biologic parent			
My other child(ren)			
My siblings			
My parents			
My other biological family members			
(If yes) Please specify: _____			

18. On a scale of 1 to 5, how important were each of the following reasons for sharing your child's genetic test results with blood relatives?

	Not at all important (1)	2	3	4	Very Important (5)
To give my blood relatives information about their genetic risk					
To encourage my blood relatives to have genetic testing					
The doctor/genetic counselor encouraged me to share the information with blood relatives					
So my relatives could make family planning decisions					
To share the information I learned because I thought it was interesting					
To share my feelings about my genetic test results					
So I could get help from blood relatives with coordinating and planning for things like appointments and other health-related responsibilities (for example, going to doctors' appointments, getting child care, getting transportation, etc.)					

19. Are there any other reasons that influenced your decision to share the results with blood relatives? _____

20. (**SKIP IF ANSWERED YES or I haven't yet, but plan to TO QUESTION 16**) On a scale of 1 to 5, how important were each of the following reasons for not sharing your child's genetic test results with blood relatives?

	Not at all important (1)	2	3	4	Very Important (5)
I do not want to worry or upset them					
I would have to talk to a blood relative I'm not close to/prefer not to talk to					
I don't have contact information for my blood relatives					

I have privacy concerns about sharing this information with my relatives					
I do not know how to explain the genetic results to my relatives					
I don't think this information is useful for my relatives					
I'm having trouble coping with my child's results					
I'm overwhelmed with my child's medication condition					
I'm worried that my relatives will treat my child differently					

21. (**SKIP IF ANSWERED YES OR I haven't Yet but plan to, TO QUESTION 16**) Are there any other reasons that influenced your decision not to share the results with blood relatives?

22. What type of information did you share with blood relatives? Please check all that apply.

- General information about the study results
- Detailed information about the genes they tested
- My relative's risk of having a condition
- Information about the possibility of being treated unfairly based on the study results
- Recommendations of ways to prevent illness
- Recommendations for more screening and testing
- Feelings about the study results
- Other, please specify: _____

23. How did you share information about your child's genetic test results with your blood relatives? Please check all that apply.

- In person
- By phone
- By letter
- By email
- Through social Media
- Other, please specify: _____

24. Did you discuss your child's genetic test results with your child's doctor(s) or health care provider(s)?

- Yes
- Not yet, but I plan to
- No and I don't plan to (**Skip to Question 26**)

25. **If you answered yes to question 24.** With whom did you discuss your child's results?

Please indicate which doctor(s) or health care provider(s) you shared results with.

- Primary care doctor (pediatrician, family doctor) or nurse practitioner
- NICU doctor or nurse practitioner
- Neurologist
- Another specialist _____

26. If you answered "no and I don't plan to", why not? _____

27. **If you answered yes to question 26.** Did your child's doctor(s) or health care provider(s) make any recommendations based on the test result?

- Yes
- No
- I don't know / don't remember

28. **If you answered yes to question 27.** If yes, what were the recommendations (check all that apply)?

- a. Start a medicine
- b. Stop a medicine
- c. Change a medicine (change a dose of medicine)
- d. Start therapy (physical therapy, speech therapy, etc.)
- e. Stop therapy (physical therapy, speech therapy, etc.)
- f. Make changes to my child's therapy (physical therapy, speech therapy, etc.)
- g. Order a medical test (x-ray, CAT scan, heart test, etc.)
- h. Cancel a medical test (x-ray, CAT scan, heart test, etc.)
- i. Refer my child to another healthcare provider
- j. Cancel a referral to a healthcare provider
- k. Change my child's diet
- l. Start my child on vitamins or supplements

29. **If you checked j.** What kind of healthcare provider(s) did your child's doctor or nurse practitioner refer him/her to? (Check all that apply)

- a. Cardiologist (heart doctor)
- b. A neurologist (brain doctor)
- c. A geneticist (genetics doctor)
- d. A nephrologist (kidney doctor)
- e. A dermatologist (skin doctor)
- f. A pulmonologist (lung doctor)
- g. An immunologist (immune system doctor)
- h. A hematologist (blood doctor)
- i. An oncologist (cancer doctor)
- j. An audiologist (hearing doctor)
- k. A dentist
- l. A social worker

- m. A hospice or palliative care program
- n. Other _____

30. Sometimes children qualify for clinical trials because they have received certain genetic test results. Was your child's doctor able to find a clinical trial for your child?

- Yes
- No
- I don't remember
- I don't know

31. **If answered no to 30.** Sometimes families find out their child doesn't qualify for a certain clinical trial because they have received certain genetic test results. Did this happen to your child because of his/her genetic test results?

- Yes
- No
- I don't remember
- I don't know

The last few questions have been asking you about what your child's doctors or healthcare providers have recommended for your child. Now we want to know which of these things you've been able to do.

32. **The following options are only presented if they were selected in the previous question (question 28).** Which of the following have you and your child been able to do so far as a result of your child's genetic results? (check all that apply)

- a. Start a medicine
- b. Stop a medicine
- c. Change a medicine

- d. Start a kind of therapy (physical therapy, speech therapy, etc.)
- e. Stop a kind of therapy (physical therapy, speech therapy, etc.)
- f. Make changes to a therapy (physical therapy, speech therapy, etc.)

- g. Get a medical test (x-ray, CAT scan, heart test, etc.)
- h. Avoid getting a medical test (x-ray, CAT scan, heart test, etc.)

- i. See another healthcare provider
- j. Avoid having to see another healthcare provider

- k. Change my child's diet
- l. Start my child on vitamins or another supplement

33. **If you checked g.** What kind of medical test(s) has your child had as a result of the genetic test results? (Check all that apply)

- a. Another genetic test
- b. Another type of blood test
- c. An X-ray
- d. An MRI

- e. A CAT scan
- f. A heart ultrasound or ECHO
- g. An ultrasound of another part of the body
- h. A test that required a surgery (such as a spinal tap or biopsy)
- i. Another kind of surgery (getting a g-tube or trach)
- j. A test of brain electricity (EEG)
- k. A test of heart electricity (EKG)
- l. A test of muscle electricity (EMG)
- m. A test of nerve electricity (nerve conduction test)
- n. Other _____

34. **If you checked i.** What kind of other healthcare provider(s) has your child seen as a result of his/her genetic test results? (Check all that apply)

- a. A cardiologist (heart doctor)
- b. A neurologist (brain doctor)
- c. A geneticist (genetics doctor)
- d. A nephrologist (kidney doctor)
- e. A dermatologist (skin doctor)
- f. A pulmonologist (lung doctor)
- g. An immunologist (immune system doctor)
- h. A hematologist (blood doctor)
- i. An oncologist (cancer doctor)
- j. An audiologist (hearing doctor)
- k. A dentist
- l. A social worker
- m. A hospice or palliative care program
- n. Other _____

35. **If at least one item was checked on 28, but no items were checked on 32.** It looks like your child's doctor or nurse practitioner recommended some things, but you haven't been able to do those things. Why is that? _____

36. **If at least one item was checked on 28, but no items were checked on 32.** Do you still plan on doing some of these things?

- Yes
- No

37. **If you responded "no" on 36.** You said you don't plan to do the things your child's doctor(s) or health care provider(s) proposed. Why is that? _____

38. Since you got your child's genetic test results, have you been told by a doctor or other healthcare provider that your child's diagnosis might affect future pregnancies in your family?

- Yes
- No
- Not applicable (I wasn't planning on having more kids)

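### Printed 4-month/4-month-plus survey: a wrong cross-reference at question 27 closes the recommendation questions, question 29 opens on the wrong option, and questions 22-23 lack a gate (minor)

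*Combined protocol and SAP*

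**What the plan says.** The form in Appendix 7.4 and 7.5 carries the Family Communication and Medical Actions measures. Section 3.f.2 (5) and Table 2 place both at one contact only, 4 months plus 2 weeks after return of results (ROR). The printed routing is as follows.

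- **Questions 24-28.** Question 24 asks whether the parent discussed the results with the child's doctors and offers Yes, not yet, or no. Question 25 opens on Yes at 24. Question 26 is open text: "If you answered 'no and I don't plan to', why not". Question 27 asks whether the doctor made recommendations and opens with "If you answered yes to question 26". Question 28 (which recommendations) opens on Yes at 27.
- **Question 29.** It asks what kind of provider the child was referred to, under the cue "If you checked j". Option j of question 28 is "Cancel a referral to a healthcare provider"; option i is "Refer my child to another healthcare provider".
- **Questions 32-37.** Question 32 (what the family has been able to do) is restricted by "The following options are only presented if they were selected in the previous question (question 28", with the bracket closing there. Questions 33 and 34 open on options g and i of 32. Questions 35 and 36 carry "If at least one item was checked on 28, but no items were checked on 32". Question 37 opens on No at 36.
- **Questions 16-23.** A parent who did not share results with relatives goes from 16 to 20; one who has not yet shared goes to 18; one with no blood relatives is told to skip everything that remains. Questions 20 and 21 carry skip cues tied to 16. Questions 22 and 23, on what was shared and how, carry none.

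**The concern.** A gate that no answer can satisfy closes its own question and everything that depends on it. Question 27 has such a gate, and behind it lies the whole sequence on what was recommended and what the family could act on. The schedule lists no later contact at which these items are asked again.

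The wording of question 32 describes which options are displayed, which makes sense only on an electronic form. The appendix therefore reads at least partly as a routing specification, and paper copies are the stated fallback (section 3.j). If the printed gates were programmed, or the cues followed on paper, recommendation and follow-through items would be missing from parents who did discuss the results. Question 29 would go to the wrong parents, and questions 22-23 would be put to parents with nothing to report.

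**Working it through.** The plan states no figure to reproduce. The check traces the printed gates, taking inputs from Appendix 7.4 and 7.5 only.

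**Step 1. Questions 24-38 (15 visible questions).**

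| Question | Opens on, as printed | Status as printed |
|---|---|---|
| 24, 30, 38 | no gate | open |
| 25 | Yes at 24 | can open |
| 26 | No at 24 | can open |
| 31 | No at 30 | can open |
| 27 | Yes at 26 (open text) | closed |
| 28 | Yes at 27 | closed |
| 29 | option j at 28 | closed |
| 32 | shows only options ticked at 28 | stem may show, no options |
| 33, 34 | options g and i at 32 | closed |
| 35, 36 | something ticked at 28, nothing at 32 | closed |
| 37 | No at 36 | closed |

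Closed: 27, 28, 29, 33, 34, 35, 36, 37 = 8. Adding 32, which cannot be answered, gives 8 + 1 = 9. The remaining 15 - 9 = 6 are 24, 25, 26, 30, 31 and 38. With question 27 gated on Yes at 24, all 15 become reachable by some path.

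**Step 2. What one parent can reach.** The counts above are unions over answers that exclude one another: 25 and 26 need different answers at 24, and 33-34 need something ticked at 32 while 35-37 need nothing ticked.

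- As printed, longest path: 24, 25 or 26, 30, 31, 38 = 5 (not counting the empty stem of 32).
- With 27 corrected, longest path: 24, 25, 27, 28, 29, 30, 31, 32, 35, 36, 37, 38 = 12.
- Greatest difference for one parent: 12 - 5 = 7. Parents who did not answer Yes at 24 lose nothing, since the corrected gate would not admit them either.

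**Step 3. Question 29.** Write (i, j) for the two referral options of 28, with 1 meaning ticked. The printed gate opens for (0,1) and (1,1); the question fits (1,0) and (1,1). Parents ticking only i are missed, and parents ticking only j are asked about a referral that was not made. Question 34, the parallel item on providers actually seen, opens on i.

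**Step 4. Questions 22-23.** Visible paths through the family block from question 16:

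- shared: 17, 18, 19, 22, 23
- did not share: 20, 21, 22, 23
- not yet: 18, 19, 22, 23
- no blood relatives: none

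Two of the four options lead to 22-23 although nothing was shared.

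**Step 5. Last option of question 16.** Read literally, it skips 17-38 = 22 visible questions: 7 (17-23) about relatives and 15 (24-38) that are not about sharing with relatives. The documents do not say how many parents would choose it.

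**The case against.** **The fielded logic is not the printed form.** Table 3 has these surveys completed online in Genome Gateway, whose branching is not in the documents. Section 3.j.1 provides weekly review of all data, section 3.n describes testing before deployment, and the manual is updated during the study. This stands as a reason not to claim data loss. It does not make the form right: testing against a faulty specification can pass, and paper users see the printed cues.

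**Nine of 15 overstates one wrong number.** This largely stands. A reader might infer that each parent loses nine answers. The nine is a union across paths, it all follows from the gate at 27, and correcting that gate restores every question.

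**Questions 22-23.** A reader might infer that sharers and non-sharers become inseparably mixed. They do not: question 16 records sharing status, and both items are tick-all-that-apply, so a non-sharer can leave them empty. What remains is needless burden and noise.

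**Blanks read as no recommendations.** Question 27 has its own No and don't-know options, so a blank is not coded as No. If the gate had been programmed literally, the item would be empty for every parent, which should be conspicuous. The misreading is possible but not likely.

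**Question 16.** Its last option may have been meant to cover only the family block, since Family Communication and Medical Actions are listed as separate measures. The wording is ambiguous, so this is a query and not a demonstrated error.

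**Conclusion.** The point holds as a minor fault, wrong as written in the printed form. Question 27 refers to a question with no Yes; question 29 is tied to the opposite of what it asks; questions 22-23 lack a gate. Taken literally, the first leaves 9 of the 15 visible questions 24-38 unanswerable across all paths, with a one-parent maximum of 5 instead of 12. The counts assume that gates are applied exactly as printed, and they cover only the visible questions, because pages after question 38 were not available. That question 27 was meant to follow Yes at 24 is inferred from its content; the form does not say so.

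A reader might go further and conclude that data were lost or that trial conclusions are affected. The documents support neither. The deployed logic is not shown. Medical Actions and Family Communication are not among the outcomes named in section 3.e.5 and do not appear in the SAP. GCOS, PUGS and PrU at ROR, and the non-inferiority tests on them, are unaffected.

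**What to change.** 1. Gate question 27 on Yes at question 24.
2. Gate question 29 on option i of question 28.
3. Route parents who have not shared results past questions 22-23: those who did not share go from 21 to 24, and those who have not yet shared go from 19 to 24.
4. Confirm what the last option of question 16 was meant to skip. If only the family block, change it to skip to question 24.
5. Compare the deployed Genome Gateway logic and any paper forms with the corrected routing. If collection has ended, as the past-tense SAP suggests, report which items were not obtained and from whom.

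The cost is three routing corrections, one wording query and one check of the survey logic, with no added visits or participants. After collection has ended, the remaining cost is the check and a short note.
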